# 7.7.

The actual date and time of collection of the blood sample will be recorded in the relevant section of the eCRF, as well as the reason in case no sample was taken.

The sample will be used for an exploratory endpoint and will be analyzed in a specialty lab.

# 7.8. Quality-of-Life and Patient-Reported Outcomes

The patient will complete the QoL questionnaire (SF-36 v2.0) and the PRO (FACT-Th6 and FACIT-Fatigue Scale) as indicated in the SoA (Table 1).

**FACT-Th6**: The FACT-Th6 uses the Likert scale, with patients rating their degree of concern in the past 7 days. The 6 selected items pertain to ability to do usual activities, worry about problems with bleeding or bruising, worry about the possibility of serious bleeding, avoidance of physical or social activity because of concern with bleeding or bruising and frustration due to the inability to carry out usual activities.

**SF-36 v2.0**: The SF-36 is a 36-item scale constructed to survey health-related QoL on 8 domains: limitations in physical activities due to health problems; limitations in social activities due to physical or emotional problems; limitations in usual role activities due to physical health problems; bodily pain; general mental health (psychological distress and well-being); limitations in usual role activities due to emotional problems; vitality (energy and fatigue); and general health perceptions.

argenx BVBA Confidential Page 78 of 162

**FACIT-Fatigue Scale**: The FACIT-Fatigue Scale is a short, 13-item, easy to administer tool that measures an individual's level of fatigue during their usual daily activities over the past week. The level of fatigue is measured by recording item responses on a 4-point Likert scale ranging from 0 "not at all" to 4 "very much."

argenx BVBA Confidential Page **79** of **162** 

### 8. STATISTICS

The statistical analyses will be performed by the sponsor's designated CRO using statistical analysis systems SAS® (SAS Institute, Cary, NC, US) version 9.4 or higher, and the software package R, if applicable. The standard operating procedures (SOPs) and work instructions of the sponsor's designated CRO will be used as the default methodology if not otherwise specified.

Any change to the data analysis methods described underneath will be mentioned in the statistical analysis plan (SAP). Any additional analysis and the justification for making the change, will be described in the clinical trial report (CTR). Additional exploratory analyses of the data may be conducted as deemed appropriate. The below paragraphs contain the main general features of the statistical analysis. More details will be provided as needed in the SAP.

# 8.1. Determinations of Sample Size

The null and alternative hypotheses are defined as  $H_0$ :  $\pi_1 = \pi_2 \ vs$ .  $H_A$ :  $\pi_1 \neq \pi_2$ , where  $\pi_1$  and  $\pi_2$  are the population probabilities to achieve a sustained platelet count response (primary efficacy endpoint) for patients with chronic ITP receiving placebo and for patients with chronic ITP receiving efgartigimod, respectively.

The response rate of placebo patients with chronic ITP reaching the primary endpoint is expected to be 60%, while for efgartigimod patients with chronic ITP a response rate of 60% is expected (ie,  $\pi_1 = 60$ 0). Given these assumptions, a total of 600 N = 117 patients with chronic ITP randomized will ensure a power of at least 90% to reject the null hypothesis at a 1-sided significance level 600 of 0.025.

For the first key secondary endpoint "extent of disease control," assuming a median cumulative number of weeks of disease control over the planned 24-week treatment period with platelet counts of  $\geq 50 \times 10^9 / L$  in the chronic ITP population of 10 weeks for patients receiving efgartigimod and 3 weeks for patients receiving placebo, a total of N=117 patients will ensure a power of  $\geq 99\%$  (two-sided  $\alpha$  of 0.05) to detect a significant difference between both treatment groups. For ensuring a power of at least 90%, a total number of N=54 patients would be needed, given these assumptions. Calculations are based on the Wilcoxon-Mann-Whitney test, where the O'Brien-Castelloe approach was taken to compute the power, taking into account a 2:1 allocation ratio to receive efgartigimod versus placebo.

# 8.2. Analysis Populations

The full analysis set (FAS) consists of all randomized patients. In general, the FAS will be used for efficacy analyses. For the primary and first key secondary endpoint the subset of all

argenx BVBA Confidential Page 80 of 162

patients in the FAS with chronic ITP will be used. The analysis will follow the intent-to-treat principle, ie, patients will be analyzed according to their randomized treatment, irrespective of the treatment they actually received.

The per protocol (PP) population is a subset of the FAS, ie, all patients from the FAS without a major protocol deviation. The PP population will be used for sensitivity analyses for the primary and key secondary endpoints.

The safety analysis set comprises all patients in the randomized population who have received at least 1 dose or part of a dose of IMP. Patients will be analyzed according to the actual treatment received for safety analyses.

# 8.3. Patient Disposition, Characteristics, and Concomitant Medication

A tabular presentation of the patient disposition will be provided. It will include the number of patients screened, randomized, received IMP treatment, completed the trial, as well as the number of early discontinuations from IMP treatment (including rescued patients) and trial, with reasons for discontinuation from IMP treatment or trial, and major protocol deviations.

A listing will be presented to describe dates of screening, screen failure with reason, randomization or assigned treatment, completion or early discontinuation, and the reason for discontinuation, if applicable, for each patient.

Patient characteristics will be listed and summarized (by treatment group and overall). Summaries will include descriptive statistics for continuous measures (number of observations, mean, standard deviation, median, 1st quartile, 3rd quartile, minimum, and maximum) and for categorical measures (frequency and percentage). Patient characteristics include, but are not limited to, age, sex, race, weight, body mass index, and baseline platelet level.

Use of concomitant medication will be summarized by treatment group with frequency and percentage. Separate summaries of concurrent ITP therapies and rescue therapy by treatment group will be provided. All concomitant medications used will be listed.

### 8.4. Statistical Methods

All patients starting at least 1 infusion of efgartigimod or placebo will be assessed for safety according to their actual treatment.

The efficacy analysis will be performed on the FAS or the subset of patients in the FAS with chronic ITP, and analyzed with intent-to-treat principle (ie, patients will be analyzed according to their planned treatment irrespective of the treatment actually received). Supportive analyses will be conducted in the PP population. The safety analysis will be performed on the safety analysis set.

argenx BVBA Confidential Page **81** of **162** 

The PK analysis set will include all patients from the safety analysis set who have at least 1 serum post-dose PK measurement.

# 8.4.1. Primary Endpoint Analysis

# Definition of the estimand for the primary endpoint

- Population: adult patients with chronic ITP, having an average platelet count of <30×10^9/L, and, at the start of the trial, either being on concurrent ITP treatment(s) and having received at least 1 prior therapy for ITP in the past, or not being on treatment for ITP but having received at least 2 prior treatments for ITP
- Variable: sustained platelet count response defined as achieving platelet counts of at least  $50 \times 10^9$ /L for at least 4 of the 6 visits between week 19 and 24 of the trial
- Main intercurrent events:
  - i. early discontinuation of treatment (prior to visit 24) due to lack of efficacy (eg, more than 3 occurrences of rescue therapy) or due to an AE
  - ii. initiation of rescue therapy at week 12 or later
  - iii. increase of dose and/or frequency of concurrent ITP therapies at week 12 or later
- Population-level summary: proportion of patients with sustained platelet count response

# Handling of main intercurrent events

A composite strategy approach will be taken to address the main intercurrent events described above. This implies that patients who discontinue treatment prior to visit 24 due to lack of efficacy (eg, more than 3 occurrences of rescue therapy) or due to an AE, as well as patients who receive rescue therapy at week 12 or later, or for whom dose and/or frequency of concurrent ITP therapies have increased at week 12 or later, will be considered non-responders for the primary endpoint analysis.

### Estimation of treatment effect and statistical inference

The primary endpoint will be analyzed using a Cochran-Mantel-Haenszel statistic test stratified for the stratification factors history of splenectomy (yes versus no), receiving concurrent ITP therapies at baseline (yes versus no), and for baseline platelet count level category ( $<15\times10^9$ /L versus  $\ge15\times10^9$ /L). The treatment effect will be presented as the odds ratio together with its 95% confidence interval (CI) and two-sided p-value. In addition, an adjusted difference of the proportions with its 95% CI will be provided.

### Handling of missing data

Missing data for reason of 1 of the main intercurrent events will be handled as described above. Details on handling other missing data will be provided in the SAP.

argenx BVBA Confidential Page **82** of **162** 

### Complementary analyses

To facilitate interpretation of the estimated treatment effect in the primary analysis, complementary analyses will be conducted where the main intercurrent events are handled differently, eg, by using the hypothetical and/or 'treatment policy' strategy. Furthermore, an exact logistic regression analysis in which the continuous baseline platelet count level is added as covariate instead of the baseline platelet count category will be conducted as supportive analysis. Details will be provided in the SAP.

# 8.4.2. Key Secondary Endpoint Analyses Subject to Alpha Control

Extent of disease control is defined as the number of cumulative weeks over the planned 24-week treatment period with platelet counts of  $\geq 50 \times 10^9$ /L. For each patient this number will be calculated by counting the number of analysis visits from week 1 until week 24 (End-of-Treatment visit) at which the platelet count level is >50×10^9/L. A Wilcoxon-Mann-Whitney test stratified by receiving concurrent ITP therapies at baseline (yes versus no), history of splenectomy (yes versus no), and baseline platelet count level category ( $<15\times10^9/L$ versus  $>15\times10^9$ /L) will be used to compare the extent of disease control between both treatment groups. The 2-sided p-value resulting from this hypothesis test will inform on whether the null hypothesis that the distributions of number of cumulative weeks for both treatment groups are identical can be rejected. The test will be conducted at a significance level  $\alpha$ =0.05. An estimate of the location shift will be provided, along with the associated 95% confidence interval. When 1 of the main intercurrent events occurs, platelet count levels measured after the occurrence will be censored (or, they will not be taken into account for the calculation of the number of cumulative weeks). In other words, they will be handled as if the platelet count level were  $<50\times10^9$ /L. Missing platelet counts because of early discontinuation due to lack of efficacy or due to an AE will be handled in the same way.

Sensitivity analyses will be conducted to assess the robustness of the analysis results to the proposed handling of intercurrent events and missing platelet counts.

Furthermore, a complementary analysis will be performed where extent of disease control is handled as a time-to-event endpoint (with "loss of disease control" being the event). Cox proportional hazards regression methodology will be applied for this complementary analysis. Details on the model and the event and censoring scheme for this complementary analysis will be provided in the SAP.

The key secondary endpoints on proportion of patients in the overall population with a sustained platelet count response and on proportion of patients in the overall population achieving platelet counts of at least  $50 \times 10^9$ /L for at least 6 of the 8 visits between week 17 and 24 of the trial will be analyzed in the same manner as the primary endpoint.

The number of bleeding events per patient (assessed using the WHO bleeding scale; where WHO scale ≥1 at any visit is considered a new bleeding event) will be analyzed using a zero-inflated negative binomial model. This model will account for the large expected number of patients with zero bleeding events. It is a mixture model consisting of 2 components: a

argenx BVBA Confidential Page 83 of 162

negative binomial count model and a binary model for predicting excess zeros. The model will consist of the number of events as the dependent variable and of randomized treatment, the stratification variables (history of splenectomy; receiving concurrent ITP therapies at baseline), and baseline platelet count as independent variables. An offset term will be used to allow for patient exposure. Both the count model, using the log link, and the binary model, using the logit link, will contain the same independent variables. The probability of no bleeding will be estimated for each randomized treatment group. A Wald test will be used to test the null hypothesis that the log of the bleeding rate ratio on placebo and efgartigimod is equal to zero against the alternative that it is different from zero. The rate of bleeding over 24 weeks on placebo and efgartigimod will be provided, along with the rate ratio, 95% 2-sided Wald-type CI, and 2-sided p-value. Missing bleeding assessments for reasons of 1 of the main intercurrent events will not be imputed, but the offset term will be adapted accordingly to reflect the assessment period until the occurrence or start of the intercurrent event. Incidence of bleeding will also be summarized descriptively by visit. Severity of bleeding will be summarized descriptively by visit. In addition, a summary of within-subject maximum severity will be provided.

The primary endpoint analysis will act as gatekeeper for the testing of the key secondary endpoints. Subject to meeting statistical significance for the primary endpoint, the key secondary endpoints will be analyzed using a fixed-sequence testing procedure to maintain the overall type I error rate at 5%. The type I error rate of each individual test will be 5%, but the test will only be conducted if the analysis for all previous endpoints in the pre-defined hierarchy resulted in a p-value <0.05. The order in the testing hierarchy of the key secondary endpoints is as follows:

- 1. The extent of disease control defined as the number of cumulative weeks over the planned 24-week treatment period with platelet counts of  $\geq 50 \times 10^9 / L$  in the population with chronic ITP.
- 2. The proportion of patients in the overall population (chronic and persistent ITP) with a sustained platelet count response defined as achieving platelet counts of  $\geq 50 \times 10^9 / L$  for at least 4 of the 6 visits between week 19 and week 24 of the trial.
- 3. The incidence and severity of the WHO-classified bleeding events in the overall population.
- 4. Proportion of patients in the overall population achieving platelet counts of  $\geq 50 \times 10^9 / L$  for at least 6 of the 8 visits between week 17 and 24 of the trial.

Complementary analyses for the key secondary endpoints will be conducted. Subgroup analyses for the primary and/or the key secondary endpoints may be conducted. Details will be provided in the SAP.

argenx BVBA Confidential Page 84 of 162

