The number of bleeding events per patient (assessed using the WHO bleeding scale; where WHO scale ≥1 at any visit is considered a new bleeding event) will be analyzed using a zero-inflated negative binomial model. This model will account for the large expected number of patients with zero bleeding events. It is a mixture model consisting of 2 components: a negative binomial count model and a binary model for predicting excess zeros. The model will consist of the number of events as the dependent variable and of randomized treatment, the stratification variables (history of splenectomy; receiving concurrent ITP therapies at baseline), and baseline platelet count as independent variables. An offset term will be used to allow for patient exposure. Both the count model, using the log link, and the binary model, using the logit link, will contain the same independent variables. The probability of no bleeding will be estimated for each randomized treatment group. A Wald test will be used to test the null hypothesis that the log of the bleeding rate ratio on placebo and efgartigimod is equal to zero against the alternative that it is different from zero. The rate of bleeding over 24 weeks on placebo and efgartigimod will be provided, along with the rate

argenx BVBA Confidential Page 21 of 162

ratio, 95% 2-sided CI, and 2-sided p-value. Incidence of bleeding will also be summarized descriptively by visit. Severity of bleeding will be summarized descriptively by visit. In addition, a summary of within-subject maximum severity will be provided.

The primary endpoint analysis will act as gatekeeper for the testing of the key secondary endpoints. Subject to meeting statistical significance for the primary endpoint, the key secondary endpoints will be analyzed using a fixed-sequence testing procedure to maintain the overall type I error rate at 5%. The type I error rate of each individual test will be 5%, but the test will only be conducted if the analysis for all previous endpoints in the predefined hierarchy resulted in a p-value <0.05. The order in the testing hierarchy of the key secondary endpoints is as follows:

- 1. The extent of disease control defined as the number of cumulative weeks over the planned 24-week treatment period with platelet counts of  $\geq 50 \times 10^9 / L$  in the population with chronic ITP.

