1.2.2 Secondary endpoints

Key Secondary Efficacy Endpoints Subject to Alpha Control:

- Extent of disease control defined as the number of cumulative weeks over the planned 24-week treatment period with platelet counts of $\geq 50 \times 10^9$ /L in the chronic ITP population.
- Proportion of patients in the overall population (chronic and persistent ITP) with a sustained platelet count response defined as achieving platelet counts of at least 50×10⁹/L for at least 4 of the 6 visits between week 19 and 24 of the study.
- Incidence and severity of the WHO-classified bleeding events in the overall population.
- Proportion of patients in the overall population achieving platelet counts of at least 50×10⁹/L for at least 6 of the 8 visits between week 17 and 24 of the study

Other Secondary Endpoints Not Subject to Alpha Control (overall population):

- Percentage of patients with overall platelet response defined as achieving a platelet count of $\geq 50 \times 10^9/L$ on at least 4 occasions at any time during the 24-week treatment period.
- Extent of disease control defined as the number of cumulative weeks until week 12, with platelet counts of $\geq 50 \times 10^9$ /L.
- Percentage of patients with overall platelet response defined as achieving a platelet count of $\geq 50 \times 10^9$ /L on at least 4 occasions at any time until week 12.
- Mean change from baseline in platelet count at each visit.
- Time to response defined as the time to achieve 2 consecutive platelet counts of $\geq 50 \times 10^{9}$ /L.
- Rate of receipt of rescue therapy (rescue per patient per month).
- Proportion of patients for whom dose and/or frequency of concurrent ITP therapies have increased at week 12 or later.
- The number of cumulative weeks over the planned 24-week treatment period with platelet counts $\geq 30 \times 10^9$ /L and at least 20×10^9 /L above baseline.

SGS	Statistical Analysis Plan	
ARGX-113-1801	Final analysis	Final 1.0 of 28MAR2022

- In patients with baseline platelet count of $<15 \times 10^{9}/L$, the number of cumulative weeks over the planned 24-week treatment period with platelet counts of $\geq 30 \times 10^{9}/L$ and at least $20 \times 10^{9}/L$ above baseline.
- Change from baseline in PROs (Functional Assessment of Chronic Illness Therapy [FACIT]-Fatigue, Functional Assessment of Cancer Therapy questionnaire-Th6 [FACT-Th6]) and QoL (SF-36) at planned visits.
- Incidence of anti-drug antibodies (ADA) to efgartigimod.

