Derivation: total number of analysis visits for which WHO bleeding scale ≥ 1 . The overall score of the bleeding events per analysis visit will be used, calculated as the maximum bleeding scale over the different body systems available per analysis visit. The data will be used as is, without taking into account intercurrent events (treatment policy strategy). Missing bleeding assessments after one of the main intercurrent events will not be imputed. For 'increase of dose and/or frequency of concurrent ITP therapies or start of a new concurrent ITP therapy' and 'initiation of rescue therapy' the whole treatment period should be taken into account. In case of rescue therapy, the bleeding events will not be imputed for 4 weeks strictly after the initiation of the therapy (the initiation of the therapy is the start date/time of the administration of the first rescue treatment for that occurrence). Missing values for reasons other than the main intercurrent events, will be imputed as described in section 4.1.2.5 (approach 3).

4) Proportion of patients achieving platelet counts of at least 50×109/L for at least 6 of the 8 visits between weeks 17 and 24 of the study in the overall population.

Derivation: A patient is considered a responder if he/she shows platelet counts of at least 50×10^9 /L for at least 6 of the 8 analysis visits between weeks 17 and 24 of the study. Intercurrent events will be handled with the same composite variable strategy as described in section 4.1.2.1. Missing values not due to intercurrent events will be handled as described in section 4.1.2.5 (approach 1).

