4.1.2.5 IMPUTATION

Missing data (platelet counts) for other reasons than the main intercurrent events will be imputed as follows:

- Approach 1: if platelet count $\geq 50 \times 10^{9}/L$ for the previous and the next analysis visit, and the previous and next analysis visit are in the treatment phase, the platelet count will be imputed with $\geq 50 \times 10^{9}/L$, otherwise with $< 50 \times 10^{9}/L$.
- Approach 2: all missing data will be imputed with $<50\times10^{9}$ /L. This will only be used as sensitivity analysis for the primary endpoint and the first key secondary endpoint.

Intermittent missing data (WHO bleeding assessment) for other reasons than the main intercurrent events will be imputed as follows:

• Approach 3: If no bleeding event for previous and next analysis visit (which can enclose several successive missing bleeding assessments), and the previous and next analysis visit are in the treatment phase, impute with no bleeding event, otherwise impute with bleeding event. No imputation will be done after the last available bleeding assessment in the treatment phase.

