4.1.3.5 ZERO-INFLATED NEGATIVE BINOMIAL MODEL

Number of bleeding events (WHO bleeding scale ≥ 1) and number of significant bleeding events (WHO bleeding scale ≥ 2) will be analyzed using a zero-inflated negative binomial model, which is a mixture model consisting of two components: a negative binomial count model (using the log link) and a binary model (using the logit link) for predicting excess zeros. The model will include the number of bleeding events (see section 4.1.2.2 and 4.1.2.3) as dependent variable, and treatment, the stratification factors and baseline platelet count (continuous) as explanatory factors. An offset term (number of visits with data on bleeding) will be used to take into account the patient exposure. The rate of bleeding over 24 weeks on placebo and efgartigimod will be reported, along with the rate ratio, 95% 2-sided Wald-type CI, and 2-sided p-value.

Missing bleeding assessments strictly after of one of the main intercurrent events will not be imputed. For 'increase of dose and/or frequency of concurrent ITP therapies or start of a new concurrent ITP therapy' and 'initiation of rescue therapy' the whole treatment period should be taken into account. In case of rescue therapy, the bleeding events will not be imputed for 4 weeks strictly after the initiation of the therapy (the initiation of the therapy is the start date/time of the administration of the first rescue treatment for that occurrence).

SGS	SGS Statistical Analysis Plan	
ARGX-113-1801	Final analysis	Final 1.0 of 28MAR2022

Missing bleeding assessments for other reasons than the main intercurrent events will be imputed as described in section 4.1.2.5 (approach 3).

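### Does the alpha-controlled bleeding test leave open which rate ratio it tests?

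*Protocol*

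**What the plan says.** The endpoint is named in SAP 1.2.2 as "Incidence and severity of the WHO-classified bleeding events in the overall population". It is third among the key secondary endpoints, so under the fixed sequence (SAP 4.1.3.1) a non-significant result stops testing of the fourth.

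The analysis counts, per patient, the visits with a WHO score of at least 1 and fits a zero-inflated negative binomial model. Protocol 8.4.2 states: "Both the count model, using the log link, and the binary model, using the logit link, will contain the same independent variables". On the hypothesis, the Protocol synopsis says "A Wald test will be used to test the null hypothesis that the log of the bleeding rate ratio on placebo and efgartigimod" is zero, and 8.4.2 repeats this. The Protocol also asks for the probability of no bleeding in each arm and for incidence by visit.

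SAP 4.1.3.5 names the covariates once. Its sentence opens "The model will include the number of bleeding events (see section 4.1.2.2 and 4.1.2.3) as dependent variable, and treatment" and goes on to the stratification factors and continuous baseline platelet count. On output it says "The rate of bleeding over 24 weeks on placebo and efgartigimod will be reported, along with the rate ratio", followed in the same sentence by the interval and p-value. On exposure it says "An offset term (number of visits with data on bleeding) will be used to take into account the patient exposure".

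SAP 4.1.2.5, approach 3, fills intermittent gaps in the bleeding assessments. A gap flanked by two visits without bleeding becomes no bleeding; "otherwise impute with bleeding event". Nothing is imputed after the last available assessment.

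**The concern.** With treatment in both parts, the model has two treatment effects: a log ratio of count means among patients who can bleed, and a log odds ratio for being an excess zero. The text tests one ratio and does not say how it is built. The count-part coefficient is what a fitted model prints directly, so a programmer might take it as the tested quantity. That coefficient takes no account of a drug effect that moves patients into the group that does not bleed. The Protocol chose this model because it expects many patients with no bleeding, so this component could matter. The choice could decide the bleeding claim and whether the fourth key secondary endpoint is tested.

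The offset raises a smaller question. Approach 3 can add imputed bleeding visits to the count. If visits with data on bleeding means observed visits only, those imputed events carry no exposure.

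**Working it through.** **1. The two candidate ratios.** Let pi be the probability of an excess zero and mu the count-part mean, with E for efgartigimod and P for placebo, ignoring covariates. Then:

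- count-part ratio = mu_E / mu_P
- overall ratio = [(1 - pi_E) / (1 - pi_P)] x (mu_E / mu_P)

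They agree only when pi_E = pi_P. The documents give no bleeding rate, dispersion, excess-zero share or effect size, so there is no plan figure to reproduce and every rate below is an assumption.

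- pi 0.3 to 0.5, count ratio 1.0: 0.5/0.7 = 0.714
- pi 0.3 to 0.6, count ratio 1.0: 0.4/0.7 = 0.571
- pi 0.3 to 0.5, count ratio 1.4: (0.5/0.7) x 1.4 = 1.000

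**2. What the choice could do to the test.** Sample size is from the documents: 117 + 39 = 156 at 2:1, so 104 against 52.

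First simulation: placebo count mean 8 over 24 visits, dispersion 0.6, no covariates, 400 trials per row (Monte Carlo standard error up to 2.5 points), two-sided 5% Wald tests, delta method for the overall ratio.

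| pi_P, pi_E, count ratio | Overall ratio | Reject, count part | Reject, overall |
|---|---|---|---|
| 0.3, 0.3, 1.0 | 1.000 | 5.0% | 4.3% |
| 0.3, 0.5, 1.0 | 0.714 | 5.0% | 32.5% |
| 0.3, 0.6, 1.0 | 0.571 | 5.8% | 66.5% |
| 0.3, 0.3, 0.7 | 0.700 | 54.5% | 46.8% |
| 0.3, 0.5, 1.4 | 1.000 | 44.8% | 6.5% |

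Second simulation: the planned covariates in both parts, mean 6 bleeding visits per placebo patient who can bleed, dispersion 0.7, counts capped at 24, overall ratio held at 0.60, 2,000 trials per cell (4,000 for the null). Each cell shows results at placebo excess zeros of 20/30/50%.

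| Share of log effect acting through excess zeros | Count part (%) | Overall (%) |
|---|---|---|
| 0% | 72/66/51 | 69/60/42 |
| 50% | 23/21/19 | 63/55/39 |
| 100% | 6/6/7 | 58/49/34 |
| no effect in either part | 6.2/6.2/6.0 | 5.6/5.7/6.0 |

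The 100% row is extreme. With 20% placebo excess zeros it needs 1 - 0.8 x 0.6 = 52% on drug and no change in counts among the rest. In the 0% row the overall test is the weaker one, by 3 to 9 points.

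**3. Which ratio the text points to.** The reported quantities are the 24-week rate on placebo, the 24-week rate on efgartigimod, and the rate ratio with its interval and p-value, in one sentence. A rate of bleeding on an arm is a property of the whole arm, (1 - pi) x mu. The count-part mean describes only a latent subgroup. The Protocol's other model-based output, the probability of no bleeding per arm, is also an arm-level quantity. A Wald test fits either reading, since it applies equally to a post-estimation contrast. The log link is stated as a property of the count part and does not define the tested ratio.

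**4. Where the definition would sit.** SAP 9.1 is the code appendix and 9.1.4 is the entry for this model. Only its heading is legible in the public copy. Neighbouring entries keep stray code fragments, so the content was removed for publication.

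**5. Covariates.** The Protocol puts them in both parts, the SAP lists them once, and SAP 6.1 declares no change to this model. There is no conflict.

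**6. Offset.** With rate = events / offset, leaving imputed visits out of the offset multiplies the ratio by about (1 - m_P)/(1 - m_E), where m is the share of visits imputed. The simulation used 200,000 patients per arm, 30% placebo excess zeros, the effect split equally between the parts, and visits in weeks 2 to 23 missing at random.

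| Missing, active / placebo | Imputed visits left out | Imputed visits counted | No missing data |
|---|---|---|---|
| 5% / 5% | 0.602 | 0.601 | not listed |
| 10% / 5% | 0.64 | 0.61 | 0.59 |
| 5% / 10% | 0.56 | 0.59 | 0.60 |

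The formula agrees: 0.61 x 0.95/0.90 = 0.64 and 0.59 x 0.90/0.95 = 0.56. With equal missingness the factor is 1. A repeat run at 5% in both arms gave 0.597 either way.

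**The case for a change.** The best case for a change is that a confirmatory test should name its quantity before unblinding, and this one does so only by inference. The two readings can give opposite answers in either direction: power can collapse if the count coefficient is used, and with pi 0.3 to 0.5 and count ratio 1.4 that coefficient rejects in 44.8% of trials although the overall rates are equal. SAP 1.8 assigns bleeding to independent programming, which needs a single target. A clarifying sentence would cost almost nothing.

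Much of this is true. The algebra is right, the readable text has no formula, and a confirming sentence would be harmless. But the damage needs the less natural reading, plus a mechanism and bleeding rates that the documents do not give. If the code already forms the overall ratio, the proposed remedy is the existing plan. Independent programming would also tend to expose two different readings.

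The appeal to intent-to-treat does not hold. Protocol 8.2 asks that patients be analysed as randomised, and both readings do so with every patient in the likelihood. Preferring the overall ratio is a choice of estimand. It fits the named endpoint better, but it loses some power if the drug acts only on counts.

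**Conclusion.** No change to the plan follows. The gap is an unwritten definition that the output sentence in the Protocol and SAP largely settles in favour of the ratio of overall 24-week rates, and that the code withheld from the public copy may settle outright. On that reading the test already captures effects on both the excess zeros and the counts.

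The size is conditional. On the other reading, and under assumed bleeding rates, power at an overall ratio of 0.60 could drop from about 39-63% to 19-23% when half the log effect acts through excess zeros. With no effect in either part, rejection is similar on both readings (6.0-6.2% against 5.6-6.0%). The primary and first two key secondary endpoints are untouched, and the Protocol reports the probability of no bleeding by arm in any case.

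The offset is a wording matter. It has no practical effect on the ratio when missingness is balanced and about 0.03 under an assumed twofold imbalance. Analysts would ordinarily count the same visits in the numerator and the exposure.
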